6.2 Participant Consent

The Participant Information Consent Form and Information Sheet (PICF) will be drawn up according to the requirements of the responsible Ethics Committee. Each potential participant will be fully informed by the Principal Investigator (PI) or a designated and trained member of his/her team of all pertinent aspects of the study and will receive the PICF that will explain in a written way:

- 1. The purpose of the study.
- 2. Study duration.
- 3. Requirements of the study (follow-up visits).
- 4. All the subject's rights as a participant in the study.

Participants will be informed that they are free to refuse participation in the study, or to withdraw from the study at any time, without compromising their medical care. All foreseeable risks and

potential benefits related to study participation which might occur will be discussed and the PI (or designated team member) will provide the subject time and opportunity to inquire about details of the study, to discuss taking part in the study with others and to decide whether or not to participate to the study. In cases of bilateral surgery, patients will be required to consent for each hip joint.

Participants will be informed that their medical records may be reviewed by representatives of the Sponsor to ensure the study is being conducted according to the protocol. They will be assured that confidentiality of personal data will be maintained at all times and access to this information will be restricted to authorised personnel only. Consent for such access will be addressed in the written informed consent document that the subject will be requested to sign.

Documentation of the informed consent process will be obtained by the use of the study related Informed Consent. Failure to obtain or improper documentation patient consent is a violation of the regulations and the study protocol. If the subject agrees to participate in the study, then the subject should sign and date the PICF before the day of surgery. However, if the PICF is signed on the day of surgery, then it needs to state that the participant was given adequate time prior to the date of surgery consider his/her participation. The Principal Investigator (or designated team member) will also sign and date the consent form to indicate that the purpose, risks and benefits of the study were explained to the participant. Any patient data – PROMs, Standard of Care (SOC) X-Rays and other clinical assessment data performed as standard of care prior to the surgery will be collected for the purpose of the study, but only after obtaining the subject's consent. A copy of the executed PICF will be given to the participant, a copy will be filed within the participant's medical records, and the original will be filed in the Investigator's Site File at the Investigator's study site.

6.3 Participant Enrolment

The point of enrolment is the time at which a subject sign and date the informed consent form. Participants who meet all eligibility criteria for the study and provide written informed consent to participate, will be considered as enrolled in the study. Each subject enrolled in the study will be recorded in the Enrolment Log. An identification code will be assigned to each enrolled patient on all data forms, in order to guarantee anonymity.

7.0 MATERIAL and METHODS

The study will be conducted by orthopaedic surgeons qualified by training, experienced in hip replacement surgeries. The Principal Investigator (PI) has responsibility to inform all the staff involved in the study about all relevant aspects and information related to the study. Assigned members of the research team at each study site will be properly trained on the study procedures according to the protocol.

An approved and updated list of all individual members (Site Delegation Log), designated, trained and supervised by the principal Investigator to perform study-related procedures or involved in any specific task, has to be kept in the Investigator Site File (ISF).

7.1 Surgical Procedure

All the operations will be performed by orthopaedic surgeons qualified by training, experienced in dual mobility hip arthroplasty surgeries and familiar with the appropriate use of the components involved in this clinical study, and according to proper standardized surgical technique. Anaesthesia, postoperative pain management and prophylactic antibiotics will be administered to the participants according to the standard practice at each study site.

7.2 Clinical Assessment and Patient Reported Outcome Measures (PROMs)

The clinical assessment is performed before surgery, at 3 months, 1 year, 2, 5, 7 and 10 years after the surgery. Preoperative assessment is used as baseline values for score improvement.

Harris Hip Score

The Harris Hip Score (HHS) is a disease-specific scoring system originally intended as outcome score after arthroplasty surgeries that include the domains of function, pain, motion, and deformity 16. The HHS is considered a clinical outcome measure. The maximum score of the absolute HHS is 100 points. Pain domain contributes 44 points, function 47, ROM 5 and absence of deformity 4 points. Function is subdivided into gait and activities of daily living. Calculation of the ROM score includes splitting the motion into categories based on utility and then multiplying the degrees of motion with a given index factor. The index scores are then added and multiplied by a factor of 0.05 to obtain the final ROM score. The ROMs of the affected hip/joint will be measured with a standard goniometer.

Oxford Hip Score

Oxford Hip Score (OHS) is a patient-centred questionnaire that is designed to assess functional ability and pain from the patient's perspective. It is a short, twelve-item questionnaire developed for completion by patients undergoing THA and is extensively referenced in the Orthopaedic literature. The OHS has been demonstrated to be highly sensitive to change in patients undergoing primary THA.¹⁷ Each of the 12 questions on the Oxford hip score presents a score decreasing as the reported symptoms increase (ie. become worse). All questions are laid out with response categories denoting least (or no) symptoms being to the left of the page (scoring 4) and those representing greatest severity lying on the right-hand side (scoring 0). This method, when summed, produces overall scores running from 0 to 48 with 48 being the best outcome.

EQ-5D-5L

The EQ-5D-5L essentially consists of 2 pages: the EQ-5D descriptive system and the EQ visual analogue scale (EQ VAS).

The descriptive system comprises five dimensions: mobility, self-care, usual activities, pain/discomfort and anxiety/depression. Each dimension has 5 levels: no problems, slight problems, moderate problems, severe problems and extreme problems. The patient is asked to indicate his/her health state by ticking the box next to the most appropriate statement in each of the five dimensions. This decision results in a 1-digit number that expresses the level selected for

that dimension. The digits for the five dimensions can be combined into a 5-digit number that describes the patient's health state.

The EQ VAS records the patient's self-rated health on a vertical visual analogue scale from 0-100, where the endpoints are labelled 'The best health you can imagine' and 'The worst health you can imagine', it is requested for the patient to simply mark an X on the scale to indicate today's health and to write the number marked on the scale in the box. The VAS can be used as a quantitative measure of health outcome that reflect the patient's own judgement.

Subject's satisfaction 4-point Likert-type scale

The overall satisfaction of the patients with the result of the surgery will be scored on a 4-point Likert-type scale with response categories consisting of very satisfied (100 points), somewhat satisfied (75 points), somewhat dissatisfied (50 points) and very dissatisfied (25 points)¹⁸. The satisfaction scale will be completed by the participant postoperatively and the first one will represent the baseline for the following visits.

7.3 Radiographic evaluation

The radiographic evaluation includes standard X-rays such as antero-posterior (AP) of the pelvis/ hip and lateral views of the affected hip before surgery and then at discharge (0-6 days), and 2 years. Any X-Ray imaging done between 0-6 days and 1 year post op will be done as per Surgeon's SOC. At further follow-ups 1, 5, 7, 10 years, X-rays are optional and/or will be taken only in case of subjective complaints such as pain or clinical symptoms warrants more investigation.

7.4 Survivorship Analysis

Survival analysis of the study devices is calculated with the use of Kaplan-Meier estimation and 95% confidence interval. The analysis will be performed with the following end points:

- Revision of the acetabular component due to dislocation
- Revision of the femoral and/or acetabular component due to failure of the stem (such as stem fracture)
- Revision of the femoral and/or acetabular component due to aseptic loosening
- Definite or probable radiographic evidence of loosening of the components (such as lysis).

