53/77 and 329/425 were MobiliT cups. Their results indicated no statistically significant differences in performance between these cups with no patients undergoing revision surgery for loosening and only 1.3 % patients (one per group) requiring post-operative surgery for dislocation, thus, postoperative implant survival at a minimum of 2 years was 98.7% for any reason. A trend which falls well within the Kaplan Meier projection of 95% of survival at 10 years after the surgery. Torres-Pérez et al 2014¹⁵, completed a review of 135 cases they had treated with the cementless MobiliT cup and a variety of different head sizes and stem implants. Mean follow-up was 32 months and mean age at surgery 82.1 years. 14 patients died with functional implants in situ. They reported 2 postoperative dislocations, 5 periprosthetic femoral fractures, 2 cup loosening and one subsided stem, plus a further 7 clinical but non implant related adverse events. Cup survival at 12 months was 97.03% (87.3-99.2%) giving a 5-year prediction of 96.7% (range 85.4-98.8%). The advanced age of this group suggests a low patient survival rate at 10 years.

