In addition, Corin is conducting an ongoing long-term PMCF study (Study Ref: 1302-T-HIPLTO-RM) in France with the purpose to collect clinical and functional scores, PROMs, and radiographic data after THR surgeries with Corin hip prostheses including dual mobility procedures with MobiliT cup and the standard polyethylene (PE) insert. A total of 1100 primary THR surgeries with the cementless MobiliT cup have been performed between June 2014 and November 2021. Most of patients are female (68.6%) with an average age at the time of surgery of 77.6 ± 8.2 years old and a BMI of 27.5 \pm 5.2. The average HHS increased from 41.1 \pm 17.7 before surgery to 93.7 \pm 8.8 at 2.5 years with 93% of the study population showing satisfactory (HHS≥80) results at 2.5 years. A substantial increase was already observed after 3 months from surgery providing excellent recovery post-surgery. The OHS improved considerably from 15.4 \pm 8.2 before surgery to 45.3 \pm 5.0 at 2.5 years. Ongoing results show that the patient's satisfaction has been achieved with overall satisfaction average score of 96.5 ± 9.0 at 2.5 years. The EQ-5D VAS scored from an average of 59.4 ± 18.4 preoperatively to 82.7 ± 15.0 at 2.5 years confirming an improved status of health. A good postoperative restoration of biomechanical parameters was observed with X-rays demonstrating good implant stability and cup integration with average cup inclination of 44.7 ± 4.5 degrees at 2.5 years. No radiolucent lines or osteolysis have been reported. Two (0.2%) cases of heterotopic ossification categorised as Brooker class III at 3 months and 2 (0.4%) at 2.5 years. A total of 62 (5.6%) postoperative complications have been reported of which 16 (1.5%) led to a revision surgery. No revisions due to dislocation were reported. Kaplan Meier Survival rate is 95.89% (95% CI: 90.08%, 98.33%) at 5 years. Ongoing results at 2.5 years seem to confirm previous published data with a significant increase in joint functionality and PROMs data. The ECiMa insert compatible with the MobiliT Cup has been added to the above-mentioned study in mid-2022 and data is being collected.

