4.2 Secondary Endpoints

Secondary endpoints include:

- Revision rate of the devices under assessment after surgery to 10-year FU.
- Kaplan-Meier survival rate up after surgery to 10-year FU.
- Incidence of intraoperative and post-operative adverse events (hip, study device or surgery related) including severity and outcome up to 10-year FU.
- Change of Harris Hip Score (HHS) from preop to 10 years after surgery.
- Change of OHS from 2 to 10 years after surgery.
- Change of EQ-5-DL from preop to 10 years with previous follow-ups.
- Patient's satisfaction after surgery using the 4-point Likert-type scale at each time-point.
- Rate of continuous, progressive and symptomatic periprosthetic radiolucent lines greater than 2mm from immediate postoperative (baseline) to 2 years.

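### The Kaplan-Meier end points in Section 7.4 omit revision for any reason, so no planned curve estimates all-cause device survival

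*Protocol*

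**What the plan says.** Section 7.4 is the only place in the protocol that defines a Kaplan-Meier failure event. It opens with "Survival analysis of the study devices is calculated with the use of Kaplan-Meier estimation and 95% confidence interval" and then continues "The analysis will be performed with the following end points". Four items follow:

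- "Revision of the acetabular component due to dislocation";
- revision of either component because the stem failed;
- revision of either component for aseptic loosening;
- definite or probable loosening on radiographs, which does not require a revision.

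Other sections bear on the same quantity:

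- Section 4.2 has two separate secondary endpoints. One is "Revision rate of the devices under assessment after surgery to 10-year FU", with no limit by cause. The other is Kaplan-Meier survival to 10 years, with no event defined.
- Section 10.1 calls for Kaplan-Meier survivorship with a 95% confidence interval, again with no event defined. It also calls for crude revision rates with 95% confidence intervals and a listing of reason, time and components.
- Section 8.4 withdraws a patient from follow-up at revision, whatever the cause. Data up to that point and the reason for revision are kept for analysis.
- Section 3.1 cites earlier experience in all-cause terms: "postoperative implant survival at a minimum of 2 years was 98.7% for any reason".

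**The concern.** Sections 4.2 and 10.1 leave the Kaplan-Meier event undefined, so a reader has to take it from Section 7.4. Several ways in which a hip can come to revision are missing there: infection, periprosthetic fracture as distinct from stem failure, pain, failure of the insert, and dislocation treated on the femoral side. In a Kaplan-Meier analysis of the listed items, a hip revised for one of these reasons stops contributing at the revision and is counted as censored, although the device has failed.

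Section 7.4 presents the result as the survival of the study devices, and Section 3.4 sends the study data into the clinical evaluation. A curve that leaves out some revisions could be taken there for all-cause survival. The insert matters in particular, because Section 3.1 gives the ECiMa insert as part of the reason for the study and no listed revision end point names it.

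**Working it through.** **1. Causes against end points (Section 7.4)**

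| Revision for | Event in any listed revision end point? |
|---|---|
| Dislocation, acetabular component revised | Yes |
| Dislocation, femoral side only revised | No |
| Stem failure | Yes |
| Aseptic loosening | Yes |
| Infection | No |
| Periprosthetic fracture without stem failure | No |
| Insert failure without loosening | No |
| Pain or other cause | No |

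Under Section 8.4 each row marked No ends follow-up, so it is a censoring in these curves.

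**2. The background figures**

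- Sponsor's ongoing study (Section 3.1): 16/1100 = 1.45%, which agrees with the stated 1.5%. On the causes of these 16 it says only "No revisions due to dislocation were reported". The first end point of Section 7.4, applied to that series, would stay at 100% with 16 hips revised. How many of the 16 fall under the other listed causes is not stated.
- 135-case series (Section 3.1): "They reported 2 postoperative dislocations, 5 periprosthetic femoral fractures, 2 cup loosening and one subsided stem". These are events. The text does not say how many of the fractures were revised, so they give no share of revisions outside the list.

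**3. Size of the gap, for illustration**

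Let S be all-cause survival and f the share of revisions with an unlisted cause. With proportional cause-specific hazards, a curve restricted to the listed revision causes estimates S^(1−f). S = 0.95 is the 10-year projection quoted in Section 3.1. The values of f are assumptions.

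| f | 0.95^(1−f) | Gap to 95% |
|---|---|---|
| 0.25 | 96.2% | 1.2 points |
| 0.50 | 97.5% | 2.5 points |
| 0.75 | 98.7% | 3.7 points |

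The gap is zero only if no revision has an unlisted cause.

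For scale, with 100 hips (Section 10.2) and complete follow-up, the standard error at 95% survival is √(0.95 × 0.05 / 100) = 0.022, or 2.2 points.

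**4. Can the crude rate stand in?**

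Assume constant hazards, 5% cumulative revision at 10 years and a share L lost by 10 years. Then λ = −ln(0.95)/10 = 0.00513, μ = −ln(1−L)/10, and the expected crude proportion is λ/(λ+μ) × [1 − 0.95 × (1−L)].

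| L (assumed) | Crude proportion revised |
|---|---|
| 20% | 4.5% |
| 40% | 3.9% |
| 60% | 3.3% |

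The crude figure falls below the 5% that an all-cause Kaplan-Meier analysis would estimate. Incomplete follow-up is to be expected: Section 6.1.1 admits patients up to age 85, and in the 135-case series 14 patients died within a mean follow-up of 32 months.

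**The case against.** The strongest reply is that no revision is lost. Section 4.2 has a revision rate without limit by cause, and Section 10.1 reports it with a confidence interval and a listing of reasons and times. A cause-specific curve labelled as such is sound. Section 7.4 does not say that its list is exhaustive, and an analysis plan that is not shown could add an all-cause curve. Kaplan-Meier survival is one of eight secondary endpoints in a study that the synopsis calls descriptive, and no threshold or sample size rests on it.

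Most of this stands, and it limits the point to a should-fix. It does not remove it. The protocol has written out a list of end points that lacks the all-cause one, and the crude rate is not a substitute over 10 years (step 4).

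Some stronger readings are tempting, but the documents do not support them:

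- A reader might infer that reported survival will be too high in every case. Section 7.4 does not say whether the four items are analysed separately or together. In a composite, radiographic loosening without revision adds events and could offset part of the gap.
- A reader might infer from the five fractures, or from the 16 revisions with none for dislocation, that a large share of revisions falls outside the list. Neither figure gives that share (step 2).
- A reader might infer that nothing planned can be set beside the cited 98.7%. The text derives that figure from the 1.3% needing surgery for dislocation (100 − 1.3 = 98.7), so it looks like a crude proportion, and the planned crude revision rate is the nearer comparator.

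**Conclusion.** The point holds as a gap in the definition of the survivorship analysis. None of the four end points in Section 7.4 estimates all-cause device survival, and no other section supplies a Kaplan-Meier end point that does. A curve limited to the listed revision causes, if read as device survival, is too favourable as soon as one revision has an unlisted cause.

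The direction follows from the text; the size does not. The range of about 1.2 to 3.7 points rests on three assumptions: 95% all-cause survival, 25% to 75% of revisions outside the list, and proportional hazards. In a study of 100 hips that is roughly one to four hips, of the same order as the standard error. Should-fix: the endpoint is secondary and descriptive, and the data for the right analysis are already collected.

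**What to change.** In Section 7.4, add as the main Kaplan-Meier end point: *first revision of any study component (cup, ECiMa insert, head or stem) for any reason*. State in Sections 4.2 and 10.1, and in the synopsis, that this is the event for the Kaplan-Meier secondary endpoint.

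Keep the four listed items as supportive analyses, each reported separately and labelled as specific to its cause, with radiographic loosening kept apart from the revision end points. Their finer handling can be left to the analysis plan. Keep the crude rate and the listing as they are.

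The cost is wording only. Reason, time and components revised are already recorded for every revision, so no new data are needed. The reported survival may be slightly less favourable.

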7.5 Adverse Events

The investigator is required to report all surgical, medical device and instrument related complications/AEs; complications/AEs affecting or related to the study hip; and deaths or serious injuries including:

- Intraoperative adverse events regardless of cause, seriousness, or outcome.
- Postoperative adverse events related to the device or study hip.
- Serious postoperative adverse events resulting in death or serious injury.

Details to be recorded in the eCRF including date of occurrence, severity, event description treatment, and outcome.

Definitions¹⁹

- An adverse event (AE) is defined as untoward medical occurrence, unintended disease or injury, or untoward clinical signs (including abnormal laboratory findings) in subjects, users or other persons, whether or not related to the investigational medical device and whether anticipated or unanticipated
 - Note 1: This definition includes events related to the investigational medical device or the *comparator*.
 - Note 2: This definition includes events related to the procedures involved.
 - Note 3: For users or other persons, this definition is restricted to events related to the use of investigational medical devices or comparators.
- 2. An adverse device effect (ADE) is defined as an adverse event related to the use of an investigational medical device
 - Note 1: This definition includes adverse events resulting from insufficient or inadequate instructions for use, deployment, implantation, installation, or operation, or any malfunction of the investigational medical device.
 - Note 2: This definition includes any event resulting from use error or from intentional misuse of the investigational medical device.
 - Note 3: This includes 'comparator' if the comparator is a medical device.
- 3. A serious adverse event (SAE) is defined as an adverse event that led to any of the following:
 - a) death,
 - b) serious deterioration in the health of the subject, users, or other persons as defined by one or more of the following:
 - 1) a life-threatening illness or injury, or
 - 2) a permanent impairment of a body structure or a body function including chronic diseases, or
 - 3) in-patient or prolonged hospitalization, or
 - 4) medical or surgical intervention to prevent life-threatening illness or injury, or permanent impairment to a body structure or a body function,
 - c) foetal distress, foetal death, a congenital abnormality, or birth defect including physical or mental impairment.

Note 1: Planned hospitalization for a pre-existing condition, or a procedure required by the CIP, without serious deterioration in health, is not considered a serious adverse event.

- 4. A **serious adverse device effect (SADE)** is defined as an adverse device effect has resulted in any of the consequences characteristic of a *serious adverse event*.
- 5. An unanticipated serious adverse device effect (USADE) is defined as a serious adverse device

effect which by its nature, incidence, severity or outcome has not been identified in the current risk assessment.

Note 1: Anticipated serious adverse device effect (ASADE) is an effect which by its nature, incidence, severity or outcome has been identified in the risk assessment.

6. A **device deficiency** is defined as an inadequacy of a medical device with respect to its identity, quality, durability, reliability, usability, safety or performance

Note 1: Device deficiencies include malfunctions, use errors, and inadequacy in the information supplied by the manufacturer including labelling.

Note 2: This definition includes device deficiencies related to the investigational medical device or the comparator.

No adverse events are anticipated as a direct result of the subject participating in this study.

Should any serious adverse device effect (SADE) occur, this will be documented by the Principal Investigator (or designated team member) and reported to the Sponsor within 1 working day of the site becoming aware of the event. The Sponsor will review and notify as appropriate to relevant competent authorities.

The study site is responsible for submitting AEs to the responsible HREC in accordance with the local HREC requirements in terms of the nature of events to be submitted and the timelines for submission. Any medical devices related adverse event will be reported to Corin immediately and subsequently to all relevant competent authorities as appropriate, in parallel, and in no later than 10 working days after the investigator first learns of the event.

SAEs that are deemed to be unexpected and related to the study will be notified to the local HREC as applicable.

